13.4. Statistical Analyses

13.4.1. General Considerations

Unless otherwise stated, all significance tests will be 2-sided using the 5% significance level. In addition, 95% confidence intervals will be provided where appropriate.

An observed-cases approach will be used for tabulations of data by visit (ie, involving only those participants who attended each specific visit).

Categorical data will be summarized using the number and percentage of participants in each category and treatment group. Continuous data will be summarized using descriptive statistics including the number of non-missing observations (n), mean, standard deviation, minimum, 25th percentile, median (50th percentile), 75th percentile, and maximum values.

All the analyses specified in the protocol will be reviewed in relation to the blinded data obtained and the SAP will be finalized before breaking the randomization code for primary analysis. Any changes from the statistical analysis planned in this clinical trial protocol will be described and justified in a protocol amendment, the SAP, and/or in the CSR.

Objectives and endpoints are provided in Section 5.

13.4.2. Multiplicity Adjustment

The analysis of secondary and exploratory endpoints will not have multiplicity adjustments.

13.4.3. Disposition of Participants

Participant disposition will be presented, including reasons for discontinuation from the trial, for all participants who provide informed consent.

13.4.4. Demographics and Other Baseline Characteristics

Demographics include age, sex, race, and ethnicity. Other baseline characteristics include height, weight, duration of COPD, past and concurrent diagnoses (from medical history and indications for concomitant medications), concomitant medications, previous COPD treatments, and substance usage.

Descriptive statistics of demographics and other baseline characteristics will be presented separately for all randomized participants, the FAS, and the PPS. The presentations will be overall and by treatment group. Demographics and other baseline characteristics will also be listed.

13.4.5. Primary Efficacy Endpoint

Formal hypothesis testing will be performed to analyze the difference in treatment failure rates between treatment groups within 28 days after randomization using the Cochran-Mantel-Haenszel test for the common risk difference stratified by severity of acute COPD exacerbation and baseline smoking status. The risk difference and the corresponding 95% CI will be presented. The null hypothesis of no difference in response rates between rademikibart and placebo will be tested against the 2-sided alternative that there is a difference at significance level 0.05. The primary efficacy analysis will be conducted based on observed data using the FAS.

13.4.5.1. Sensitivity Analyses

Sensitivity Analysis 1: Missing data from participants who discontinue the trial prior to a documented treatment failure will be considered to have experienced treatment failure. The primary analysis will be repeated using this sensitivity analysis to handle missing data.

Sensitivity Analysis 2: Tipping point analyses will be conducted whereby the primary analysis on the binary endpoint will be repeated for every possible scenario regarding the missing

endpoints. Every possible combination of response and non-response in the Rademikibart dose and placebo groups is considered for the missing values, and the primary analysis is repeated for each scenario. A plot of p-values will be provided, and the robustness of the primary result will be assessed.

13.4.5.2. Supplementary Analyses

The primary analysis will be repeated on PPS.

13.4.6. Secondary Efficacy Endpoints

The rate of moderate and severe COPD exacerbations in the 28 days after randomization will be analyzed using a negative binomial regression model adjusting for randomization stratification factors and baseline characteristics. Full details of the model will be documented in the SAP.

The time to the first moderate or severe COPD exacerbation will be analyzed using a stratified log-rank test, adjusting for the randomization stratification factors. A Kaplan-Meier plot of the time to first moderate or severe COPD exacerbation will be provided.

A mixed model repeated measures analysis will be used to compare treatment groups with respect to the mean CFB in E-RS: COPD through Week 1, Week 2, and Week 4; and with respect to the absolute CFB in post-BD FEV₁ at Day 3, Week 1, and Week 4. The mixed model repeated measures model will include fixed factors for scheduled visit, treatment, the visit by treatment interaction, and will include covariates for the stratification factors and the respective baseline value of the continuous outcome. An unstructured covariance matrix will be used to model the within-participant covariance structure.

The FAS will be used for the secondary endpoint analyses.

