admission) that, in the opinion of the Investigator, would interfere with evaluation of the IP or interpretation of trial results.

20. Current acute COPD exacerbation for which SoC was started >48 hours prior to Screening Visit 1b.
21. Chest X-ray or computed tomography (CT) scan at Screening Visit 1b reveals evidence of clinically significant abnormalities not believed to be due to the presence of COPD, or a clinically significant pulmonary infection (chest radiograph demonstrating consolidation) identified by chest X-ray (CT scan) at Screening Visit 1b.
22. Participants with a prolonged QTc interval (male >450 msec, female >470 msec, Fridericia correction); any other clinically significant abnormalities in electrocardiogram (ECG) at Screening, in the opinion of the Investigator.
23. An alanine aminotransferase (ALT) or aspartate aminotransferase (AST) level $\geq 2.5 \times$ the upper limit of normal (ULN) and/or bilirubin level $\geq 1.5 \times$ ULN at Screening Visit 1b.
24. Any other acute illness other than the acute COPD exacerbation at the start of the trial at Visit 1b.
25. Any clinically significant abnormal findings in physical examination, vital signs, hematology, clinical chemistry or urinalysis which, in the opinion of the Investigator, may put the participant at risk because of their participation, or may influence the results of the trial or their ability to complete the duration of the trial.
26. Female participant who is pregnant, lactating or breast-feeding, or has a positive urinary β -hCG test prior to randomization.
27. Evidence of clinically significant non-respiratory active infection, including ongoing chronic infection.
28. Receipt of any marketed nonbiologic drug that modulates type 2 cytokines (eg, suplatast tosilate) 30 days or 5 half-lives prior to randomization, whichever is longer.
29. Receipt of any marketed (eg, dupilumab or other monoclonal antibody) or any investigational biologic for COPD or other diseases within 16 weeks or 5 half-lives prior to randomization, whichever is longer.
30. Live, attenuated vaccinations within 4 weeks prior to randomization or planned live, attenuated vaccinations during the trial.
31. Treatment with oral corticosteroids and/or hospitalization for an exacerbation of COPD (not for the index acute COPD exacerbation) completed less than 4 weeks prior to randomization.
32. Donation of blood, plasma or platelets within 90 days prior to randomization.

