10.3. Spirometry

Spirometry will be performed according to American Thoracic Society (ATS)/European Respiratory Society (ERS) guidelines (Miller et al. 2005; Graham et al. 2019) at the timepoints specified in the SoA (Table 5). Spirometry assessments, including FEV₁, and FVC (both the absolute measurement and the percentage of predicted normal value will be recorded), should be made as close to the scheduled timepoints as possible. In addition, protocol-specified clinic spirometry must be completed in accordance with the lifestyle restrictions as defined in Section 7.3.

Spirometry will be performed preferably in the morning; afternoon is allowable in the exceptional circumstance when morning spirometry cannot be performed. Current smokers need to be reminded not to smoke for at least 1 hour before spirometry. For each participant, the same spirometer and standard spirometric techniques, including calibration, will be used to perform spirometry at all visits and, whenever possible, the same person should perform the measurements.

Baseline FEV₁ is defined as the post-BD FEV₁ performed at Visit 2 before IP administration. If Visit 1b and Day 0 (Visit 2) are the same day, then post-BD spirometry does not need to be repeated.

At the timepoints SoA (Table 5), if the participant's condition allows, post-BD FEV₁ will be conducted approximately 15 to 30 minutes after the participant-administers 4 inhalations of albuterol (salbutamol) via MDI (ie, total of 400 mcg) using a spacer device.

It is anticipated that participants who are randomized into the trial will receive albuterol (salbutamol) as part of the routine treatment of the acute COPD exacerbation during Visit 2. In this case, spirometry should be scheduled to coincide with this treatment to allow post-BD recordings to be measured.

For hospitalized participants, post-BD spirometry should also be performed at the timepoints specified in the SoA (Table 5), including V3 and V4, provided the participant's condition allows.

Hospitalized participants discharged from the hospital prior to Visit 3 and Visit 4, or participants that were not hospitalized for the index COPD exacerbation, should return to the trial site or have a home health care visit for spirometry assessments at Visit 3 and Visit 4 when feasible.

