10.5.4. Exacerbations of Chronic Pulmonary Disease Tool

Exacerbations of Chronic Pulmonary Disease Tool – Patient-Reported Outcome (EXACT-PRO) is a PRO instrument designed to capture information on the occurrence, frequency, severity, and duration of exacerbations of disease in patients with COPD ([Leidy et al. 2011](#); [Leidy et al. 2014](#)). EXACT-PRO captures information on the severity of the respiratory and systemic manifestations of a COPD exacerbation as reported by the patient ([Leidy et al. 2011](#)). Development and validation history of the tool is consistent with guidelines proposed by the FDA, European Medicines Agency (EMA), and well-known measurement principles.

The instrument is a daily diary composed of a total of 14 items representing the following domains:

- Breathlessness (5 items),
- Cough and sputum (2 items),
- Chest symptoms (3 items),
- Difficulty bringing up sputum (1 item),
- Tired or weak (1 item),
- Sleep disturbance (1 item), and
- Scared or worried (1 item).

The instrument is to be completed every evening (typically at bedtime) using an e-diary. However, at Visit 2 (Randomization) only, the EXACT-PRO is to be completed as the first assessment before randomization and hence can be completed in the morning or afternoon. The daily recording of information allows an assessment of the underlying day-to-day variability of a

participant's symptoms and facilitates the detection of symptom worsening indicative of a COPD exacerbation. The total score for EXACT-PRO ranges from 0 to 100. The EXACT total score assesses COPD exacerbations. The higher the score, the more severe are the symptoms.

The Evaluating Respiratory Symptoms in COPD (E-RS: COPD) consists of 11 items from the 14-item EXACT-PRO instrument. E-RS: COPD is intended to capture information related to the respiratory symptoms of COPD (ie, breathlessness, cough, sputum production, chest congestion, and chest tightness). The E-RS has a scoring range of 0 to 40 (Leidy et al. 2014). Three subscales of the E-RS: COPD are used to describe different symptoms; dyspnea, cough and sputum and chest symptoms.

In addition to the collection of EXACT-PRO, participants will also complete daily e-diary questions to provide information on other symptoms suggestive of exacerbation, such as sputum purulence (color), wheezing, sore throat, colds (nasal discharge and/or nasal congestion), and fever without other cause.

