- For participants who consent to participate in the trial during the urgent healthcare visit for an acute COPD exacerbation, Visit 1b should be completed immediately after providing written informed consent and verifying eligibility.

b The Screening Period after Screening Visit 1b is up to 48 hours. Any procedures completed as part of the assessment and treatment of the COPD exacerbation may be used for Screening (eg, hematology, clinical chemistry, urinalysis, β -hCG if applicable, spirometry, chest X-ray or CT, ECG). Note that the maximum combined number of chest X-rays and/or CT scans must not exceed 2 for screening.

c Randomization/Baseline Visit is defined as Day 0 (Visit 2). Screening Visit 1b and Day 0 (Visit 2) may be the same day or up to 48 hours apart. If Visit 1b and Day 0 (Visit 2) are the same day, then FeNO and post-BD spirometry do not need to be repeated. For ECG, complete physical exam, and height/weight the Visit 1b assessment will serve as Baseline. All assessments at Visit 2 (Day 0) are to be conducted pre-IP dose administration with the exception of the assessment of SC injection sites and post-IP administration vital sign measurements.

d Visit 3 and Visit 4 are for participants who are hospitalized for current acute COPD exacerbation. Hospitalized participants discharged from the hospital prior to Visit 3 or Visit 4, or participants that were not hospitalized, should return to the trial site or have a home health care visit for spirometry assessments at Visit 3 and Visit 4 when feasible.

e At Visit 7, participants will be contacted by telephone.

f Medical history includes COPD history, COPD exacerbation history, past and current medical conditions (including cardiovascular and cerebrovascular medical history, surgical history), and substance usage.

g Participants will be trained on home use of the e-diary at Visit 2 and throughout the trial on an as needed basis. Participants will complete the assessment of EXACT-PRO every evening, and Dyspnea NRS and usage of short-acting rescue medications via e-diary twice daily at home.

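### The MMRM in Section 13.4.6 gives baseline a single slope for all visits, which may cost some precision at Week 4

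*Protocol*

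**What the plan says.** Protocol Section 13.4.6 specifies one MMRM for two secondary endpoints: change from baseline in E-RS: COPD (Weeks 1, 2 and 4) and in post-BD FEV1 (Day 3, Weeks 1 and 4). Visit and treatment enter as main effects, and the list of terms then runs: "the visit by treatment interaction, and will include covariates for the stratification factors and the respective baseline value of the continuous outcome". No baseline-by-visit term is listed. On the covariance, the section says: "An unstructured covariance matrix will be used to model the within-participant covariance structure".

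On when baseline is measured:
- Section 10.3 defines baseline FEV1 as the post-BD value "performed at Visit 2 before IP administration".
- Section 10.5.4 says that at Visit 2 "the EXACT-PRO is to be completed as the first assessment before randomization". The E-RS is scored from that instrument.
- Section 7.2, criterion 20, excludes a "Current acute COPD exacerbation for which SoC was started >48 hours prior to Screening Visit 1b".
- Appendix A, footnote c, says "Screening Visit 1b and Day 0 (Visit 2) may be the same day or up to 48 hours apart".

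Baseline is therefore a pre-dose value taken during the index exacerbation. It can fall up to about 48 + 48 = 96 hours after standard care began.

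**The concern.** A baseline main effect with no visit interaction makes baseline predict every visit with the same slope. In a stable population that is often harmless. Here participants enter in an exacerbation and recover over four weeks, so an acute-phase value may track Day 3 or Week 1 closely and Week 4 less well.

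With unstructured covariance, the pooled slope is weighted toward the visits that baseline predicts most tightly, which are then the early ones. The early slope is carried to Week 4 and over-adjusts it. What is at stake is precision in the Week 4 FEV1 and E-RS comparisons, which the collected data could recover.

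**Working it through.** **The plan's own figure.** The protocol states no power, SD or correlation for FEV1 or E-RS. Its only power statement concerns treatment failure (22.5% vs 45%, 152 evaluable, two-sided 5%). With 76 per arm this gives 84.2% by the pooled normal approximation and 80.0% by Fisher's exact test, so the stated 80% or more reproduces. It has no bearing on this point.

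**Method.** Let r be the vector of true baseline slopes by visit, R the between-visit covariance, and S = R − rr′ the residual covariance given baseline (all variances set to 1).
- Pooled slope under the listed model: b = (1′S⁻¹r) / (1′S⁻¹1).
- Variance of the visit-t treatment contrast, common slope relative to visit-specific slopes: 1 + (r_t − b)² / S_tt, with S_tt = 1 − r_t².

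**Worked case, FEV1, moderate decline (assumed).** Baseline correlations are 0.85 / 0.75 / 0.60 at Day 3 / Week 1 / Week 4. Between-visit correlations are 0.85 (Day 3–Week 1), 0.70 (Day 3–Week 4) and 0.80 (Week 1–Week 4).
- The weights on the three visit slopes are 0.753, 0.145 and 0.102, so b = 0.753×0.85 + 0.145×0.75 + 0.102×0.60 = 0.810.
- Week 4: (0.60 − 0.810)² / (1 − 0.60²) = 0.0441 / 0.64 = 6.9%.
- Day 3 and Week 1 lose under 1% each.

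**Range over assumed correlations**

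| Endpoint | Baseline correlations | Between-visit correlations | Pooled slope | Excess Week 4 variance |
|---|---|---|---|---|
| FEV1, flat | 0.80/0.80/0.80 | 0.85/0.85/0.85 | 0.800 | 0% |
| FEV1, mild | 0.85/0.80/0.70 | 0.85/0.75/0.85 | 0.818 | 2.7% |
| FEV1, moderate | 0.85/0.75/0.60 | 0.85/0.70/0.80 | 0.810 | 6.9% |
| FEV1, steep | 0.90/0.70/0.40 | 0.80/0.50/0.70 | 0.867 | 26% |
| E-RS, mild | 0.60/0.50/0.40 | 0.80/0.70/0.80 | 0.536 | 2.2% |
| E-RS, moderate | 0.65/0.50/0.35 | 0.80/0.65/0.80 | 0.574 | 5.7% |
| E-RS, steep | 0.70/0.45/0.20 | 0.75/0.50/0.75 | 0.600 | 17% |

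Between-visit correlations are in the order first–second, first–third, second–third visit.

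Other assumed patterns give the same picture. Correlations of 0.90/0.80/0.60 give 12 to 13%, depending on the between-visit correlations; 0.80/0.60/0.40 gives 21%; 0.70/0.50/0.30 gives 16%; 0.85/0.75/0.65 gives 4%; 0.90/0.85/0.80 gives 1%.

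The slope matters, not the correlation. If the SD rises during recovery (0.45 at baseline, then 0.48, 0.50, 0.55), correlations of 0.85/0.75/0.65 correspond to slopes of 0.91/0.83/0.79, and the loss is only 1.0%.

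**In power terms.** For a comparison with 80% power under visit-specific slopes, power under the common slope is Φ(2.802/√VR − 1.960), where VR is the variance ratio. This gives 78.9% at VR 1.027, 77.3% at 1.069 and 70.4% at 1.259.

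**Simulation check.** The common-slope model was simulated with 76 per arm, complete data and 8,000 runs per scenario. Week 4 variance ratios were 1.02, 1.08 and 1.24 (FEV1 mild, moderate, steep) and 1.05 (E-RS moderate). Bias was about zero, and type I error was 4.6 to 5.1%.

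**E-RS as cumulative means.** Suppose the Week 4 value averages the period, weighting the Week 1, 2 and 4 values 1/4, 1/4 and 1/2. The pooled slope does not change. In the moderate case the Week 4 slope becomes 0.25×0.65 + 0.25×0.50 + 0.5×0.35 = 0.4625, with residual variance 0.624. The excess is (0.4625 − 0.574)² / 0.624 = 2.0%, down from 5.7%. The same steps take the mild case from 2.2% to 0.6% and the steep case from 17% to 7%.

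**Missing data.** All three simulations assume no true effect.
- About 21% missing at Week 4, depending on baseline in the same way in both arms (correlations 0.90/0.80/0.60): the mean common-slope estimate was −0.005 (Monte Carlo SE 0.004), so no bias.
- 19% missing on placebo by baseline and 10% on active at random (correlations 0.85/0.75/0.60): 0.032 SD with the common slope, against 0.004 SD with visit-specific slopes.
- Baseline-missingness relation reversed between arms: −0.07 SD.

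The protocol plans for 5% dropout, well below the missingness in these simulations.

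**The case against.** The strongest reply is that Section 13 calls itself a summary and leaves complete details to the SAP. Listing some terms does not rule out others, and baseline-by-visit is a common SAP-level refinement. This has some force, since the SAP may already contain the term. But 13.4.6 expressly defers the full negative binomial model to the SAP and does not do so for the MMRM, where it names factors, interaction, covariates and covariance. Section 13.4.1 treats a departure from the planned analysis as a change to be described and justified. The listed model is therefore open to comment.

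Three stronger readings are tempting, and the documents do not support them.
- A reader might infer that baseline is taken at the peak of the exacerbation. Nothing says so, and treatment may have been running for up to about 96 hours.
- A reader might infer that precision is certainly lost. It is not lost if the slope is constant, and the protocol gives no figure for choosing among the scenarios.
- A reader might infer that missingness related to baseline severity biases the Week 4 contrast. When that relation is the same in both arms, randomization keeps baseline balanced among those observed and the slope error cancels.

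It is also fair to say that these are secondary endpoints with no stated power and no multiplicity control.

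**Conclusion.** The point holds as a minor one about efficiency. As written, the 13.4.6 model applies one baseline slope to all visits. If that slope falls between the early visits and Week 4, which is plausible but not shown, the Week 4 comparison is less precise than the data allow. Mild to moderate decline raises the standard error by about 1 to 4%. In the tabulated steep cases (17% and 26% excess variance) it rises by 8 to 12%. All sizes rest on assumed correlations.

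The listed analysis is valid with complete data. The possible bias needs baseline-dependent missingness that differs between arms, and it was small in the cases tried.

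**What to change.** In Section 13.4.6, add a baseline-by-visit interaction to the MMRM terms for post-BD FEV1 and E-RS: COPD, and do so before unblinding. With three visits, three slopes replace one, which costs two degrees of freedom with about 152 evaluable participants. No new data are needed, and almost nothing is lost if the slope proves constant.

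Section 13.4.7 lists no MMRM terms, so nothing there needs correcting. Using the same model for the exploratory endpoints would be for consistency only.

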8.4.2. Randomization

All participants meeting enrollment criteria will be randomized at baseline (Day 0) to receive treatment with either rademikibart 600 mg SC or volume-matched placebo.

As participants qualify for randomization, they will be assigned to treatment by the IRT System. The random treatment assignments will be done in a 1:1 ratio. Randomization will be stratified by severity of the index acute COPD exacerbation (requiring hospitalization or not [yes/no]) at Baseline, and smoking status at Baseline (current or former).

See Section 7.4 for details on screen failures.

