11.1.4. Demographic/Medical and Surgical History and Other Baseline Characteristics

Demographic information collected will include age and sex, along with ethnicity and race as described by the participant. Other baseline characteristics include height, weight, and body mass index. Medical history includes COPD history, acute exacerbation history, past and current medical conditions (such as cardiovascular and cerebrovascular medical history and surgical history), and substance usage.

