11.2.2. Height and Weight

Height and weight will be measured at time points per the SoA (Table 5). Height will only be measured at Screening Visit 1a or 1b. The participant's height must be measured without shoes and weight must be determined in indoor clothing and without shoes.

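### The mixed model for post-bronchodilator FEV1 leaves out age, sex and height, which are already recorded; adding them would probably buy a little precision at Week 4

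*Protocol*

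**What the plan says.** Protocol Section 13.4.6 uses one mixed-model specification for two outcomes, the E-RS: COPD score and FEV1. The FEV1 comparison is made "with respect to the absolute CFB in post-BD FEV₁ at Day 3, Week 1, and Week 4". The fixed terms are scheduled visit, treatment and their interaction, and the model "will include covariates for the stratification factors and the respective baseline value of the continuous outcome". The covariance matrix is unstructured.

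The strata come from Section 8.4.2: "Randomization will be stratified by severity of the index acute COPD exacerbation" (hospitalization required or not), together with current or former smoking.

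Section 10.3 fixes the baseline: "Baseline FEV₁ is defined as the post-BD FEV₁ performed at Visit 2 before IP administration".

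The omitted variables are collected. Section 11.1.4 states "Demographic information collected will include age and sex" and "Other baseline characteristics include height, weight, and body mass index". Section 11.2.2 adds "Height will only be measured at Screening Visit 1a or 1b", so height is known before dosing. Section 10.3 also says of FEV1 and FVC that "both the absolute measurement and the percentage of predicted normal value will be recorded".

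**The concern.** FEV1 in litres depends on body size, age and sex; the protocol relies on this when it records percent of predicted. A baseline FEV1 would absorb most of that dependence if it measured a person's usual lung function closely. Here it is taken during the index exacerbation, after treatment has begun, so it mixes usual lung function with an acute deficit that differs between people. Week 4 FEV1 should lie nearer the recovered level. Age, sex and height can therefore still predict Week 4 FEV1 once baseline is in the model.

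What is at stake is the width of the confidence interval for a secondary endpoint in a trial of about 160 participants. Adjusting for variables measured before dosing does not bias a randomized comparison, so any precision they offer is cheap to take.

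**Working it through.** **The plan's own figures.** The protocol states no standard deviation, correlation, effect size or power for FEV1, so there is nothing to reproduce for this endpoint. The evaluable number does follow: 160 × 0.95 = 152. The power statement in Section 13.2 concerns treatment failure only. It reproduces (84.2% at 76 per arm, against at least 80% stated) and is not touched by this point.

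**Assumed inputs** (none is in the protocol):
- r², the share of between-person variance in recovered FEV1 explained by age, sex and height: 0.2 to 0.4, middle 0.3.
- c, the correlation of baseline with observed Week 4 FEV1: 0.7 to 0.9, middle 0.8.
- Reliability of the Week 4 measurement: 0.9.
- The gap between baseline and the recovered level is unrelated to age, sex and height.

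**Formulas.** Scale the recovered level S to variance 1.
- Measurement variance at Week 4: m = (1 − 0.9)/0.9 = 0.1111.
- Squared correlation of baseline with S: ρ² = c²/0.9. Noise variance of baseline: e = 1/ρ² − 1.
- Residual variance as planned: 1/(1 + 1/e) + m.
- Residual variance with age, sex and height: 1/(1/(1 − r²) + 1/e) + m.

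With baseline in the model, these residual variances are the same for change from baseline as for the Week 4 value.

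**Middle case** (c = 0.8, r² = 0.3):
- ρ² = 0.64/0.9 = 0.7111, e = 0.4063, 1/e = 2.4615.
- As planned: 1/3.4615 + 0.1111 = 0.4000.
- With the covariates: 1/(1.4286 + 2.4615) + 0.1111 = 0.3682.
- Ratio 0.920, so 8.0% lower.

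**Smallest gain** (c = 0.9, r² = 0.2):
- ρ² = 0.9, 1/e = 9.
- As planned: 1/10 + 0.1111 = 0.2111. With the covariates: 1/10.25 + 0.1111 = 0.2087.
- Ratio 0.988, so 1.2% lower.

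**Largest gain** (c = 0.7, r² = 0.4):
- ρ² = 0.5444, 1/e = 1.1951.
- As planned: 1/2.1951 + 0.1111 = 0.5667. With the covariates: 1/(1.6667 + 1.1951) + 0.1111 = 0.4605.
- Ratio 0.813, so 18.7% lower.

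**Cost of three parameters.** At 152 evaluable this is a factor of 145/142 = 1.021.
- Middle: 0.920 × 1.021 = 0.940, a 6.0% reduction. The standard error ratio is √0.940 = 0.970, about 3% smaller.
- Smallest: 0.988 × 1.021 = 1.009, a 0.9% loss.
- Largest: 0.813 × 1.021 = 0.830, a 17.0% reduction.

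**Cross-checks, also on assumed inputs.**
- A single-visit simulation (152 participants, 12 scenarios, 3,000 replicates each) built FEV1 in litres as a fraction of a value predicted from age, sex and height. The variance of the treatment difference changed by a factor of 0.79 to 0.99, below 1 in every scenario.
- A grid in which predicted FEV1 correlates equally (0.4-0.6) with baseline and follow-up gave net factors of 0.88 to 1.01, about 1 when baseline and follow-up correlate at 0.9.
- After the parameter cost, a comparison with 80% power would move to about 81% if the covariates explain 5% of the remaining variance, and to about 83% if they explain 10%.

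**The case against.** The strongest reply is that nothing here is wrong. Baseline plus stratification factors is a standard, valid model with its type I error intact, and FEV1 is a secondary endpoint with no power claim and no multiplicity control. That stands, and it limits the point to an efficiency suggestion. A reader might infer from the omission that the FEV1 comparison is biased or invalid; the documents do not support that.

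A second reply is that the detail belongs to the SAP. Section 13 calls itself a summary and Section 13.4.1 allows changes to be described in the SAP, so the SAP may already add these covariates. But Section 13.4.6 expressly defers the negative binomial model to the SAP, while its mixed-model paragraph names the terms and makes no such deferral. The point is therefore about a stated specification.

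Other stronger readings also fail:
- **A larger gain.** Applying 0.7-0.9 to the error-free Week 4 level gives 3-21%, middle 10%, which a reader might convert to about 16 of 160 participants. That is not the correlation one observes, and it ignores the parameter cost.
- **Baseline at the worst point of the exacerbation.** The protocol does not say this. Standard care may start up to 48 hours before Visit 1b and Visit 2 may follow up to 48 hours later, so some baselines fall about four days into treatment. Partial recovery would raise the correlation and shrink the gain.
- **The same gain at all visits.** Only Week 4 was computed. Day 3 FEV1 probably tracks Day 0 more closely, so the gain there may be smaller.
- **The exploratory models too.** Section 13.4.7 fixes no covariates, and its outcomes include percent-predicted FEV1, which is already expressed against a predicted normal.

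**Conclusion.** The point holds as a small, nearly free improvement. The FEV1 model in Section 13.4.6 omits three prognostic variables that the trial already records. On the assumptions above, adding them changes the Week 4 variance by between a 1% loss and a 17% reduction after the parameter cost. The middle case is about 6%, or a standard error about 3% smaller, and there is no net gain if baseline and Week 4 FEV1 correlate near 0.9.

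The direction is well founded, but the protocol supplies none of the inputs that set the size. The calculation also treats Week 4 as a single-visit analysis and does not model the full repeated-measures fit. The primary endpoint, the sample size and the validity of the planned FEV1 analysis are unaffected.

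**What to change.** Before unblinding, add age, sex and height as prespecified fixed covariates to the post-bronchodilator FEV1 mixed model of Section 13.4.6, in the protocol or the SAP. The cost is one sentence and three model parameters, with no new data. Timing matters because covariates chosen after unblinding would not be credible. Leave the E-RS: COPD model as it is, which means giving the two outcomes separate covariate lists. Section 13.4.7 needs no change.
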